Block randomization with a block size of four (4) will be used at each site. Each site will receive sets of well-shuffled envelopes in packets of four. A given packet will be completed before the next packet is opened. Each packet of four will contain two cards specifying that a subject should be in the active treatment arm and two cards specifying the placebo arm. This procedure results in six possible different arrangements, for four patients, of the ordering of treatment and placebo assignments. The unblinded Pivotal Study coordinator will record the patient's designation but will not share the assignment with the patient, Investigator, or Statistician.

4) Pivotal Study Schedule; Subject Enrollment and Activities; Monitoring

The Pivotal Study Period will last one hundred and twelve days, beginning with a Pre-Treatment Baseline Period of one Month (28 days), at the end of which the Investigator will reconfirm the appropriateness of the subject's participation in the Pivotal Study, followed by a Treatment Period of three Months (84 days).

As noted, subjects will be advised that during the Pivotal Study Period they may maintain patterns of usage of approved therapeutic medications that they normally use and that they should not initiate new medications, medicating patterns or other interventions. Accommodations for rescue medications will be made, using pharmaceuticals from an approved list developed by the Investigators.

Potential participants will be required to keep a Daily Headache Diary throughout the Pivotal Study Period and, *inter alia*, to document times of CVS-M treatments. They will enter the Daily Headache Diary information using a computer-based system.

The phases and activities of the Pivotal Study are listed below:

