- Treatment Period: The eighty-four days (3 Months) following the Pre-(iii) treatment Baseline Period constitute the Treatment Period. This is the test period, the results from which will be measured against the Pre-Treatment Baseline Period data. Specifically, data from the last Month of the Treatment Period will be compared with the Monthly data from the one-month-long Pretreatment Baseline Period. Roughly two weeks after the start of treatment, a Pivotal Study clinical visit will occur and another Visit Assessment form will be completed, treatment delivery data from the CVS-M Device will be collected, and a Quality of Life and Cognition Assessment exam will be performed. A Vestibular Testing Procedure will be completed. A second usability questionnaire will be completed. The patient will be asked to bring the CVS-M Device to the clinic to perform a treatment in front of the Pivotal Study coordinator to reaffirm proficiency in using the Device. Any issues related to balance or other safety concerns will promptly be referred to both the relevant Investigator and the Vestibular System Consultant, either of whom can terminate the patient's further participation in the Pivotal Study if necessary.
- (iv) Return of CVS-M Device & clinic visit: At the end of the Treatment Period the patient will be asked to return the CVS-M Device and a Quality of Life and Cognition Assessment exam will be performed. A Vestibular Testing Procedure will be completed. A third usability questionnaire will be completed. All remaining treatment delivery data from the CVS-M Device will be collected.

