CVS has been used extensively and safely in the practice of medicine since its discovery more than a century ago by [name], a discovery for which he received the Nobel Prize in Physiology/Medicine in 1914. There have been no reports in the literature of adverse events or significant negative side effects associated with CVS. The side effect profile from use of the CVS-M Device is expected to be the same as that associated with diagnostic CVS procedures.

CVS-M acts on the central nervous system via the vestibular organs. This mechanism is distinctly different from most forms of neurostimulation that involve either electrical currents applied directly to a target nerve or region (implanted neurostimulators) or a diffuse current to larger areas of the cortex (TMS, CES, tDCS). CVS is non-invasive and easily employed. The SNS CVS-M Device enables its therapeutic use and utility by controlling thermal induction and providing safeguards that ensure treatments remain firmly within parameters established by the supervising physician.

The Berg Balance test (Berg et al.) is well-established and widely used in clinical settings to asses a person's static and dynamic balance abilities. *Inter alia*, the Test is used to quantify clinical improvement or deterioration in patients -- from evaluation of "normals" to assessment of individuals with a wide range of balance impediments. The long form Test consists of 14 balance- related tasks ranging from standing up from a sitting position to standing on one foot. Each task is graded from 0 - 4, and the final measure is the sum from all elements of the Test:

- 41-56 = low risk of fall
- 21-40 = medium risk of fall
- 0-20 = high risk of fall

The Berg Balance test will provide a consistent and easily administered, task-based scheme for identification and quantification of deterioration, if any, of a subject's balance that could be associated with use of the CVS-M Device. The local clinical coordinators will undergo training on administration of the Berg test prior to the Study. Abnormal findings with the Berg test may lead to a more extensive vestibular assessment evaluation. No unexpected side effects, nor any adverse events, have occurred in prior studies utilizing the CVS-M Device.

7) Pivotal Study Endpoints

• Primary Efficacy Endpoint for the Pivotal Study

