For active-treatment subjects as a group: During the third Month of the Treatment Period, their average total number of Monthly Migraine Headache Days will be lower than their comparable averages derived from the Pre-Treatment Baseline Period.

• Secondary Efficacy Endpoints for the Pivotal Study

- The number of active-treatment subjects having a reduction of 50% or more in Migraine Headache Days during the third Month of the Treatment Period as compared with the Pre-Treatment Baseline Period will exceed the number of placebo-treatment patients having that response rate.
- For active-treatment subjects as a group: During the third Month of the Treatment Period, their average Total Monthly Headache Pain Scores will be lower than their comparable averages derived from the Pre-Treatment Baseline Period.
- For active-treatment subjects as a group: During the third Month of the Treatment Period, their average number of Treated Headaches will be lower than their comparable averages derived from the Pre-Treatment Baseline Period.
- For active-treatment subjects as a group: On average, in comparison with their Pre-Treatment Baseline Period, they will have at the end of the Treatment Period, improvement in scores associated with the Quality of Life and Cognition Assessment measures.

• Safety Endpoint for the Pivotal Study:

The principal safety endpoint for the Study is to verify the absence of material dizziness, with the associated risk of falls, as a consequence of using the active-treatment Device. The Berg Balance test will be used to assess any changes in balance performance as a result of Device usage. Transient nausea and minor dizziness may be experienced by patients, as is sometimes reported in the diagnostic CVS literature, and patients will be trained to verify balance stability after a treatment and before standing up. Previous pilot studies using the Device did not identify nausea or dizziness as side effects attributable to the Device, based on patient self-reporting.

8) Calculating Total Monthly Headache Pain Scores

For each subject the following Total Monthly Headache Pain calculations will be made:

- a. Using the Daily Headache Diary data from the Pre-Treatment Baseline Period, the cumulative Pain Scores for all of the days on which the subject had a Headache during the Month will be calculated; and
- b. For the third Month of the Treatment Period, the cumulative Pain Scores for all of

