• Impact with respect to usage of abortive pain medications and co-morbid conditions such as nausea, dizziness, photophobia and phonophobia will be assessed based on the subjects' Daily Headache Diary entries and the Visit Assessments performed by the Investigators and their designates. An assessment will be made by the blinded Statistician as to whether there is evidence of acute or

sustained alterations in the listed measures and co-morbidities during the Treatment Period as separately compared with the Pre-Treatment Baseline Period.

- Data collected from the Quality of Life and Cognition Assessment questionnaires will be utilized for two purposes. Scoring and analysis will be performed by a single, highly experienced, blinded Neuropsychologist. Analysis first will involve review for safety, with protocols being reviewed for *changes* from baseline on the order of one standard deviation or greater on cognitive measures (using published data) and declines indicating clinical change on affective measures. Triggering during this review will prompt a broader review for consideration of withdrawal due to negative effects. Analysis will then secondarily involve pilot comparisons between Treatment and Placebo groups with respect to *changes* in scores across measures. While the present Study is not powered for detection of treatment effects on cognitive/affective measures, the acquired data can serve as pilot work to identify promising areas for future research.
- The following null hypothesis and alternative hypothesis will be evaluated for the Total Monthly Headache Pain secondary endpoint:
 - "There is no difference between the Total Monthly Headache Pain scores (during the third Month of the Treatment Period as compared with the Month during the Pre-Treatment Baseline Period) when comparing subjects treated with the Treatment Device and subjects treated with Placebo Device."
 - "There is a reduction in Total Monthly Pain scores (during the third Month of the Treatment Period as compared with the Month during the Pre-Treatment Baseline Period) when comparing subjects treated with the Treatment Device and subjects treated with Placebo Device."

10) Quality Assurance Monitor

An independent quality assurance monitor will be used to audit Pivotal Study Sites.

11) References:

ICDH-2: (2004). "The International Classification of Headache Disorders: 2nd edition." Cephalalgia 24 Suppl 1: 9-160.

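### The principal safety question is causal, but no active-versus-placebo comparison is specified for it, and the two on-treatment Berg tests are given by coordinators who know the arm

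*Combined protocol and SAP*

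**What the plan says.** **Endpoint and instrument.** Section 7 sets the safety aim as to "verify the absence of material dizziness, with the associated risk of falls, as a consequence of using the active-treatment Device" and adds: "The Berg Balance test will be used to assess any changes in balance performance as a result of Device usage". It gives no threshold for what counts as material, no test and no contrast between arms.

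**Scoring.** Section 6 describes 14 observed tasks: "Each task is graded from 0 - 4, and the final measure is the sum from all elements of the Test". It assigns the work to site staff: "The local clinical coordinators will undergo training on administration of the Berg test prior to the Study".

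**Who knows the arm.** Section 3 states: "The unblinded Pivotal Study coordinator will record the patient's designation". Under section 4(ii) the local coordinator opens the envelope at the first clinic visit and files plots of the delivered temperatures in the patient records. Under section 4(iii) the patient is asked at the 2-week visit "to perform a treatment in front of the Pivotal Study coordinator". Section 5 gives session lengths of about 19 minutes (active) and about 4 minutes (placebo).

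**Schedule.** The section 12 table has all patients tested at the start of the baseline period, at the 2-week visit and at the end. Its action rule for the Berg is change from the subject's own baseline exam.

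**Analysis.** Section 9 gives the Vestibular System Consultant a blinded analysis and summary of the vestibular data without naming a contrast; the Definitions add that the consultant reviews the results. For co-morbid symptoms, including nausea and dizziness, section 9 has the blinded Statistician look for acute or "sustained alterations in the listed measures and co-morbidities during the Treatment Period as separately compared with the Pre-Treatment Baseline Period".

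**The concern.** A change from baseline in the active arm mixes the device effect with everything else that changes over the same weeks. Two such influences are visible in the documents.

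- Section 5 has all patients told that they may notice slight nausea or dizziness. Expectation can raise reports in both arms, and a before-after comparison would charge this to the device.
- Section 9 treats nausea and dizziness as conditions accompanying migraine. If the device reduces migraine, these symptoms may fall with it and offset dizziness that the device causes.

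Practice on a repeated balance test, or ordinary decline, would also be read as a device effect or would hide one. The placebo arm is there to separate these, and its Berg data are collected. The omission stands out because the same section does plan arm comparisons for Total Monthly Headache Pain and for the cognitive and affective measures.

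The second problem is upstream of the analysis. An observer-graded score recorded by someone who knows the arm can be shaded either way, and later blinded reading works from that recorded score. At stake is whether the trial can support its principal safety statement.

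**Working it through.** **Is there a planned figure to reproduce?** Not for safety. The section 9 table (72, 54, 44, 50, 40, 32) concerns the responder rate only. It reproduces exactly with the pooled two-proportion formula at two-sided 0.05 and 80% power, and has no bearing here. Section 9 asserts that the cohort is adequate for adverse events without a rate or calculation.

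**Which Berg scores are exposed?** The first test is at the start of the baseline period (section 12). The envelope is opened later, at the first clinic visit (section 4(ii)). So 2 of 3 scores per patient are exposed: 160 of 240 with 80 completers (2 × 80 of 3 × 80).

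**What each contrast estimates.** For a 28-day Month let M be the number of headache days, *a* and *b* the chance of dizziness on a headache day and on a headache-free day, *s* the extra reporting from expectation (equal in both arms if patients stay blinded), and δ the extra caused by the device. With a common baseline M₀:

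- Active change from baseline: (M_A − M₀)(a − b) + 28(s + δ)
- Placebo change from baseline: (M_P − M₀)(a − b) + 28s
- Difference between arms: (M_A − M_P)(a − b) + 28δ
- Difference between arms per headache-free day: δ

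The before-after contrast carries both *s* and the headache term. The between-arm contrast removes *s*, but keeps a headache term that is negative if the device works and a > b. Splitting by headache and headache-free days removes that term too. The split conditions on something that treatment can change, so it belongs beside the overall difference and does not replace it.

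**Precision at 40 per arm** (half of 80; two-sided 0.05 assumed, since the plan states no alpha).

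- Mean Berg change: standard error of the difference = SD × √(2/40) = 0.224 SD. The 95% half-width is 1.96 × 0.224 = 0.44 SD. The difference detectable with 80% power is (1.960 + 0.842) × 0.224 = 0.63 SD.
- No events in 40 active patients: the upper limit of the two-sided 95% interval is 1 − 0.025^(1/40) = 8.8%; the one-sided 95% bound is 1 − 0.05^(1/40) = 7.2%.
- Exact power of the Pearson chi-square test for a material balance decline. All rates are assumptions.

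| Placebo | Active | Power |
|---|---|---|
| 5% | 15% | 35% |
| 5% | 20% | 57% |
| 5% | 25% | 76% |
| 5% | 30% | 89% |
| 10% | 30% | 63% |

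**What rater bias could do** (illustration only). Take true rates of 20% active and 5% placebo. If a quarter of active-arm declines go unrecorded, the observed rate is 0.75 × 20% = 15% and power falls from 57% to 35%. If half do, it is 0.50 × 20% = 10% and power is 15%. In the other direction, if the true rate is 5% in both arms and an alert rater lifts the recorded active rate to 15%, the first row gives a 35% chance of a false signal.

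**The case against.** The best defence is that the documents are silent rather than wrong, and that the Berg is not the only safeguard. The vestibular data get a blinded analysis. Balance concerns at the 2-week visit go to the Investigator and the consultant, both blinded. Abnormal Berg findings may lead to fuller assessment. Dizziness is also captured from blinded patients' diaries and from Visit Assessments. All of this stands. It shows other routes by which dizziness can come to light, but none of them masks the scoring of the Berg or supplies a between-arm estimate.

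Several stronger readings are tempting and are not supported:

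- *The plan judges the Berg before-against-after and discards the placebo arm.* The Berg group contrast is unspecified. The own-baseline wording in section 12 is an action rule for individuals, and the baseline comparison in section 9 concerns symptoms and medication use.
- *Every Berg score is compromised.* The baseline test precedes allocation.
- *The bias will hide dizziness.* Nothing in the documents fixes its direction.
- *The 2-week Berg should follow the observed session.* The order is indeed not set. But a post-session test would no longer match a baseline test done without a session, and the 19 versus 4 minute sessions could reveal the arm to a masked rater. This is a trade-off and not a defect.

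A fair criticism of the remedy is that a plain between-arm count of dizziness days would still be confounded by fewer migraines; hence the split by day type. The Definitions entry for the diary lists pain and treatment times but no dizziness item, although section 9 relies on diary entries for it, so the split depends on what the form records.

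**Conclusion.** The concern holds in two limited parts. First, a causal safety endpoint has no specified active-versus-placebo comparison; the only references stated are baseline ones. Second, the 2-week and final Berg tests are given by staff who know the arm, and blinded review does not undo bias already in the scores.

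The size of any bias or masking cannot be derived, since the documents give no Berg distribution, dizziness rate or measure of rater error; the event and miss rates used above are illustrations. What can be said is that at about 40 per arm precision is modest (about ±0.44 SD for Berg change), so a non-significant difference would not verify absence.

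This rests on reading the local clinical coordinators of section 6 as the local Pivotal Study coordinators of section 4(ii); no separate Berg assessor is named. It should be corrected, but it does not show that the device is unsafe or that dizziness would go unnoticed.

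**What to change.** 1. State in section 9 that the principal safety analysis is the between-arm difference, with 95% confidence interval, in Berg change from baseline to 2 weeks and to end of treatment. Do the same for dizziness as recorded in the diary or Visit Assessments, overall and separately for headache and headache-free days where the diary allows. Report it as an estimate with its interval, not as a test whose non-significance is taken as proof of absence. The cost is analysis wording only for the Berg, which is already collected in both arms. For dizziness the sponsor should first confirm what the diary records.

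2. Where feasible with existing staff, have the 2-week and final Berg scored by the Investigator, whom section 3 already keeps blinded. The Investigator should not watch the session or see the temperature plots, so those plots need to be kept apart from the records used at these visits. The cost is some Investigator time. Where this is not feasible, say in the protocol and the report that on-treatment Berg scoring was unblinded.

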All participants will be patients whose response to prior therapies has been partially successful, but limited, and whose disease state and current course represent risk for eventual refractoriness but who have not yet become fully refractory. As defined in detail below, under International Headache Society (IHS) guidelines all of these patients will be classified as "episodic" or acute. None will be classified as "chronic." In assessing the effectiveness of the SNS CVS-M Device, the Pivotal Study will consider both (1) a patient's number of Headaches as well as (2) the severity of each and of all of those Headaches. The current design path involves evaluating those two disease factors both separately and on a blended basis. The primary endpoint is based on a traditional measure with which both the FDA and the medical profession are quite familiar: outcomes data collected during the Treatment Period vs. baseline data from the Pre-Treatment Baseline Period, focusing on comparative number of Migraine Headache Days. Additionally, the concept of blending those two disease measures into one quantitative assessment will be introduced: a Total Monthly Headache Pain score. As defined below, that Monthly measure will be the cumulative maximal Headache Pain Scores for all Headache Days (days on which the patient's Headache Pain level is one or higher on an eleven-point scale) during the Month in question – thus, a quantitative indication of Total Monthly Headache Pain. Study data can (and will) also be analyzed using other metrics, as described below.

For the Pivotal Study to demonstrate efficacy from SNS CVS-M Device treatments, the therapy must provide prophylactic and/or abortive-response benefits for patients. (However, for clarity, CVS-M is viewed as providing adjunctive prophylactic therapy.) Experience from IRB-approved pilot studies indicates that beneficial preventive effects and diminished incidence and severity of Headaches are achieved through daily CVS-M treatments, but not necessarily beginning immediately upon the first treatment. For that reason, patients will be treated for three Months and only the Headache burden during the last Month will be used for comparison with baseline data.

Description of the Treatment Paradigm and Study

1) Intended Use/Indication for Use

- **Intended Use:** The SNS CVS-M Device is intended to stimulate the vestibular system via external ear canals using controlled thermal waveforms.

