the days on which the subject had a Headache during the Month will be calculated.

At the conclusion of the Pivotal Study, Total Monthly Headache Pain score comparisons will be made for each subject: Pre-Treatment Baseline Period vs. the third Month of the Treatment Period. Additionally, such Total Monthly Headache Pain scores for the active-treatment subjects as a group will be compared with those for the placebo-treatment subjects as a group.

9) Statistical Analysis and Pivotal Study Size

As noted above, an experienced, independent and blinded Statistician will be utilized to analyze and summarize the Daily Headache Diaries for all patients. Also, as noted, a blinded Neuropsychologist will analyze and summarize the Quality of Life and Cognition Assessment data, and a Vestibular System Consultant will perform a blinded analysis and summary of the data from the Vestibular Testing Procedures.

Summary of the analytical methodology to be used for the Primary Endpoints

- No prospective stratification: Based on the inclusion and exclusion criteria, there is no medical reason to stratify the Pivotal Study's episodic migraine population.
- **Statistical method**: The Pearson's chi-square test will be used to evaluate the null hypothesis, which is that "There is no difference between the number of Migraine Headache Days (during the third Month of the Treatment Period as compared with the Month during the Pre-Treatment Baseline Period) when comparing subjects treated with the Treatment Device and subjects treated with Placebo Device."

The corresponding alternative hypothesis is that: "There is a reduction in Migraine Headache Days (during the third Month of the Treatment Period as compared with the Month during the pre-Treatment Baseline Period) when comparing subjects treated with the Treatment Device and subjects treated with Placebo Device."

We seek to power the Study so as to reject the null hypothesis and accept the corresponding alternative hypothesis. The following power calculations are based on probabilities from binomial distributions (2-sided test):

- Assumed efficacy metric (response rate): a reduction of 50% or more in Migraine Headache Days with respect to baseline.
- Assumed range of efficacy measured in the placebo arm: 10-15%
- Assumed range of efficacy measured in the treatment arm: 45-55%

Treatment efficacy	Placebo efficacy	Statistical power	Total minimum
			cohort size
45%	15%	80%	72
50%	15%	80%	54
55%	15%	80%	44
45%	10%	80%	50

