50%	10%	80%	40
55%	10%	80%	32

The ONSTIM (occipital nerve stimulator) study (Saper et al.) recorded a placebo (preset stimulation) efficacy of 6% and a responder rate (reduction of 50% or more in headache frequency) of 39%. Results from the PREMICE study (Cefaly, supraorbital transcutaneous neurostimulation) cited by Lambert listed a placebo efficacy of 12.1% and a responder rate of 37%. Both studies evaluated between 60-70 patients. Therefore, the range of 10-15% for placebo efficacy is felt to be relatively conservative as compared with other recent studies involving neuromodulation devices addressing Migraine Headache. The assumed efficacy rate range for the CVS Device is based on non-statistically significant observations in the two previous Migraine pilot studies. We therefore conclude that a total Study size of 80 patients is likely to be sufficient for the most probable outcomes, as that number exceeds the minimum in the table above for the most likely treatment and placebo efficacy cases. For comparison, Topiramate (Topamax) used as a prophylactic migraine treatment reports responder rates in the 37-54% range and a placebo response in the low 20% range. Therefore CVS-M responder rates in the 45-55% range would be clinically meaningful.

• **Cohort size**: Each of the sites will enroll subjects with an overall goal of 80 patients. Once up to 80 subjects have completed the Pivotal Study successfully, enrollment in the Pivotal Study will be stopped (at least temporarily) and the data will be analyzed and summarized. Using expected levels of efficacy for the Treatment and Placebo Devices, this cohort size will likely be more than adequate to demonstrate statistical significance and reject the null hypothesis. The cohort size is also expected to be adequate to establish the low rate of unanticipated adverse events associated with usage of the Device. The Sponsor may choose to extend the Study, with IRB approval, should it be necessary to increase the patient cohort size.

Summary of analytical methodologies to be used for additional safety assessments and for the Secondary Endpoints:

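### The listed primary endpoint is a before-after change in the active arm, but the hypothesis is between arms and the test and power are for a secondary responder endpoint; no rule says which result decides

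*Combined protocol and SAP*

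**What the plan says.** Section 7 (Primary Efficacy Endpoint) concerns active-treatment subjects as a group. In treatment Month 3, "their average total number of Monthly Migraine Headache Days will be lower than their comparable averages derived from the Pre-Treatment Baseline Period". The placebo arm does not appear.

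Two other places use the baseline framing without mentioning a placebo comparison. The Background describes the primary endpoint as "outcomes data collected during the Treatment Period vs. baseline data from the Pre-Treatment Baseline Period". Section 4(iii) says that "data from the last Month of the Treatment Period will be compared with the Monthly data from the one-month-long Pretreatment Baseline Period".

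Section 7 then lists the 50% responder comparison as the first secondary endpoint. This one is between arms: the number of active responders "will exceed the number of placebo-treatment patients having that response rate".

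Section 9, under its methodology for the primary endpoints, says that Pearson's "chi-square test will be used to evaluate the null hypothesis". That null is of no difference in the number of Migraine Headache Days "when comparing subjects treated with the Treatment Device and subjects treated with Placebo Device". The power calculation rests on a different quantity: "Assumed efficacy metric (response rate): a reduction of 50% or more in Migraine Headache Days with respect to baseline". On cohort size, Section 9 concludes that "this cohort size will likely be more than adequate to demonstrate statistical significance and reject the null hypothesis". It specifies a two-sided test but no alpha.

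**The concern.** Three different primaries can be read from the plan:

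1. a before-after change in mean days in the active arm (Section 7);
2. a between-arm difference in days (the Section 9 hypotheses);
3. a between-arm difference in responder proportions (the Section 9 test and power table).

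The chi-square test and the power table agree with each other. They do not agree with the listed endpoint, and the hypotheses name days rather than responders. Chi-square fits responder counts, not mean days.

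A before-after fall in one arm does not separate a device effect from placebo response or time trend. Regression to the mean may add to the change, but its direction is uncertain because entry requires 4 to 14 days, a window bounded at both ends. A device no better than placebo could therefore meet the listed primary endpoint while the between-arm comparison fails, and the plan does not say which result governs.

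Three secondary endpoints share the active-arm-only wording. For Total Monthly Headache Pain, Sections 8 and 9 supply a between-arm comparison. For Quality of Life and Cognition, Section 9 supplies one as unpowered pilot work. For Treated Headaches none is stated; Section 9 assesses abortive medication use only against baseline.

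**Working it through.** **Step 1. What the sample size was built for.** Inputs from Section 9: responder rates of 45–55% (active) and 10–15% (placebo), two-sided test, 80% power. Allocation is 1:1 (Section 3). Alpha is assumed to be 0.05. The per-arm formula, with pooled variance under the null and no continuity correction, is

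n = [1.960·√(2p̄(1−p̄)) + 0.842·√(p₁(1−p₁)+p₂(1−p₂))]² / (p₁−p₂)²

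For 45% v 15%, p̄ = 0.30:

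n = [1.960·√0.42 + 0.842·√0.375]² / 0.09 = 35.4, rounded up to 36 per arm, 72 in total.

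| Active v placebo | Plan's total | Recomputed total | Exact chi-square power, 40 per arm |
|---|---|---|---|
| 45% v 15% | 72 | 72 | 85.2% |
| 50% v 15% | 54 | 54 | 93.3% |
| 55% v 15% | 44 | 44 | 97.5% |
| 45% v 10% | 50 | 50 | 96.0% |
| 50% v 10% | 40 | 40 | 98.6% |
| 55% v 10% | 32 | 32 | 99.6% |

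All six rows reproduce, so the table is sound. It powers the first secondary endpoint. The listed primary endpoint has neither a test nor a power calculation. The last column is by binomial enumeration of the uncorrected Pearson test.

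**Step 2. How easily the Section 7 wording is met when the device does nothing.** The documents give no SD, no paired test and no expected fall in the placebo arm, so this is an illustration. Assume 40 per arm, equal devices, both arms falling by d days, and SD of change s.

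- Literal wording (mean simply lower): probability Φ(d·√40/s). For d = 1.0, s = 3: Φ(2.108) = 98.2%. For s = 2.5 and 4: 99.4% and 94.3%.
- Two-sided 5% paired t-test in the active arm, significant fall (noncentral t, 39 df): 53.8% for s = 3; 69.4% and 33.8% for s = 2.5 and 4.
- Literal wording met while a two-sided 5% two-sample t-test does not favour active (100,000 simulated trials per SD): about 96% for s = 3; 97% and 92% for s = 2.5 and 4.
- Paired test significant while the two-sample test does not favour active (simulated likewise): about 51% for s = 3; 67% and 32% for s = 2.5 and 4.

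The size of the common fall drives these results. At s = 3:

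| Common fall | Literal wording met | Paired t significant |
|---|---|---|
| 0 days | 50% | 2.5% |
| 0.5 day | 85% | 18% |
| 1.0 day | 98% | 54% |
| 2.0 days | nearly 100% | 98% |

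By contrast, with 40 per arm and equal responder rates of 10–20%, the between-arm chi-square test rejects in 5.1% to 5.9% of trials, whatever the common fall in days.

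**Step 3. What 40 per arm supports if mean days is primary.** A two-sided 5% two-sample t-test has 80% power for 0.634 SD: 1.6, 1.9 and 2.5 days for assumed SDs of 2.5, 3 and 4.

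**The case against.** The strongest reply is that the intent is visible. The trial is placebo-controlled, the only test given for the primary sits in Section 9 and is between arms, and the cohort size is judged against rejecting that null. On this reading, Section 7 is a badly worded label. The Background and Section 4(iii) are not limited to the active arm and would also fit a between-arm comparison of change from baseline. Alpha is readily inferred, since 0.05 reproduces the table.

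Much of this is fair. Section 9 does point to the between-arm comparison, and the Background and Section 4(iii) are only weak support. But intent inferred from Section 9 contradicts the explicit wording of Section 7 and is not a success rule. It also leaves open whether days or responders are tested. The authors wrote a between-arm endpoint for responders in the same section and placed it among the secondaries.

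The illustration also has limits. The 98% takes the wording at face value, with no test. The 96% is close to built in, because with equal devices about 97.5% of trials cannot significantly favour active. The paired test is not in the plan. The results depend on the assumed fall, which is why it is varied above. None of this changes the conclusion that the literal endpoint gives little protection once both arms improve.

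**Conclusion.** The concern holds and must be fixed. The success criterion of this randomised pivotal trial is not defined consistently, and its literal form ignores the control arm. This is an error of specification, not of sample size: the power table is correct for the responder comparison.

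Under an assumed common fall of 1.0 day and SDs of 2.5 to 4, an ineffective device meets the Section 7 wording in 94% to 99% of trials. The figure is 50% with no fall and nearly 100% with a 2-day fall (SD 3). These percentages rest on assumed values; the mismatch between Sections 7 and 9 does not. Confidence is high.

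**What to change.** State one between-arm primary endpoint in Sections 7 and 9, with its test, alpha and power, and say that efficacy is claimed only if that test is significant in favour of active. Two options:

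- **(a) 50% responder rate, active v placebo.** This fits the chi-square test and the existing table and needs no new data or patients. The 85.2% to 99.6% power requires all 80 completers, whereas Sections 3 and 9 allow up to 80. At 32 per arm, 45% v 15% gives about 77%.
- **(b) Between-arm difference in change in Migraine Headache Days.** Replace chi-square with a test for means, for example baseline-adjusted, and redo the power with a stated SD. The present sample-size justification no longer applies; whether 80 patients suffice depends on the assumed SD and effect.

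Restate Total Monthly Headache Pain, Treated Headaches, and Quality of Life and Cognition as between-arm differences, keeping the last as unpowered. Report within-arm changes as descriptive only.

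The cost is text edits under (a), plus a new sample-size calculation under (b). Under either, success is harder to achieve than under the present Section 7 wording.
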